10.5 Efficacy Results

10.5.1 Primary Efficacy Analysis

Results of the Sande Frequency and Sande Severity Score at Week 8 (absolute values as well as changes from baseline) will be summarized descriptively by treatment group. For the primary analysis LOCF is applied as described in section 8.2.7. The exploratory p-value and estimates for treatment effect as well as treatment group difference resulting from the ANCOVA analysis specified in section 9.2 will be reported in addition. Primary analysis will be performed on the FAS.

For supportive purposes, this analysis will be repeated for the PPS to investigate the effect of protocol deviations on the results.

A similar analysis will be performed for the Sande Frequency and Sande Severity Score (without imputation) at Week 4, Week 8 and Week 12. Baseline values will also be summarized. This analysis will be performed for the FAS only.

All data on Sande Scores will be listed on the FAS, indicating clearly imputed values.

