10.2 Sample size and power considerations

Sample size was calculated by assuming both for severity and frequency a mean difference from baseline SANDE score of -30 ± 20 in the rhNGF groups versus -20 ± 20 in vehicle group (80% power, $\alpha = 0.05$; 2-sided t-test), considering that the active comparator has already proven safe and effective in dry eye patients. Therefore, the sample size has been calculated based on a 2:1 randomization scheme by the following formula:

$$n_1 = (0.5) \times n \times (1 + k)$$

$$n_2 = (0.5) \times n \times (1 + (1/k))$$

With n_1 = active treatment, n_2 = vehicle, $n = 63$, and $k = n_1/n_2 = 2/1=2$. Therefore, $n_1 = 94.5$ and $n_2 = 47.25$. Assuming a 5% dropout rate, a total of 100 patients will be enrolled in the active arm, and 50 in the vehicle arm.

Since this is an exploratory study, no adjustment has been made for multiplicity of SANDE parameters, neither has it been taken into account that the actual analysis will be descriptive only.

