4.6 Sample Size estimation

Sample size was calculated by assuming both for severity and frequency a mean difference from baseline SANDE score of -30 ± 20 in the rhNGF groups versus -20 ± 20 in vehicle group (80% power, $\alpha = 0.05$; 2-sided t-test), considering that the active comparator has already proven safe and effective in dry eye patients.

Testing hypotheses are:

H0: mean change from baseline rhNGF = mean change from baseline Vehicle = 0

H1: mean change from baseline rhNGF = mean change from baseline Vehicle = -10

Therefore, the sample size has been calculated based on a 2:1 randomization scheme for inference with Student t test for independent groups using PS Power and Sample Size Calculations (<http://biostat.mc.vanderbilt.edu/PowerSampleSize> Version 3.0, January 2009 Copyright © 1997-2009 by William).

If the true difference in the experimental and control means is 10 (estimated from our internal study), we will need to study 96 experimental subjects and 48 control subjects to be able to reject the null hypothesis that the population means of the experimental and control groups are equal with probability (power) 0.8 and with standard deviation of 20. The Type I error probability associated with this test of this null hypothesis is 0.05.

Considering a 5% drop out, 150 patients will be included in the study: 100 patients in rhNGF group and 50 patients in vehicle group.

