- In the study protocol, no inferential analyses are specified. However, purely exploratory 95% confidence intervals and hypothesis testing for the difference between treatment groups will be implemented in the SAP on sponsor’s request. These inferential procedures will be purely exploratory without adjusting for type I error rate.
- Note to File (“NGF0216 Sande Questionnaire Endpoints”, dated 25SEP2017) clarified the administration instructions of the SANDE questionnaire.

5 General Definitions

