8.2.7 Efficacy Variables

Primary and Secondary Endpoints: Sande Score

The Symptom Assessment in Dry Eye (SANDE) questionnaire is a short questionnaire to evaluate both dry eye intensity and frequency by using a 100 mm visual analogue scale (VAS). The patient symptoms of ocular dryness and/or irritation will be quantified on the scale based on two questions that assess both severity and frequency of symptoms.

For the assessment, the patients mark on the 100 mm VAS line the point that they feel represents their perception of their current state. The VAS score is determined by measuring in millimeters from the left hand end of the line to the point that the patient marks. The SANDE scores will be then evaluated for the 2 questions severity (0-100) and frequency (0-100).

The Note to File (“NGF0216 Sande Questionnaire Endpoints”, dated 25SEP2017) clarifies the administration instructions of the SANDE questionnaire.

The Sande score will be assessed at Baseline, Week 4, Week 8 and Week 12 visit and is recorded on the eCRF page ‘Symptoms Assessment in Dry Eye’. At each visit, only one assessment is performed aggregating the situation for both eyes (i.e. no separate assessment per study eye).

Primary endpoint will be defined as:

- Change from Baseline in Sande frequency score at Week 8
- Change from Baseline in Sande severity score at Week 8,
i.e. Week 8 score recorded on the eCRF minus the Baseline score on the eCRF

If at least one Sande assessment is missing at Week 8, the values of the last post-baseline assessment (including those from unscheduled visits) with non-missing values for frequency and severity will be imputed (LOCF). No imputation is performed in case of a missing baseline value (as defined in section 8.1).

Additionally, Sande frequency and severity scores as well as respective changes from Baseline will be evaluated without any imputation for Week 4, Week 8 and Week 12, respectively.

Secondary Endpoints: Ocular Surface Staining (NEI Scale)

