9.2 Specific Methods for Efficacy Analyses

As a general principle, all secondary efficacy analyses will be performed for the study eye only. Efficacy data in non-study eye will be listed.

For the primary and secondary endpoints, mean change from baseline will be compared between treatment groups for the study eye. The null hypothesis will be tested that there is no difference between rhNGF and vehicle in the mean overall change from baseline between both treatments:

$$H_0: \mu_{\text{rhNGF}} = \mu_{\text{Vehicle}}$$

$$H_1: \mu_{\text{rhNGF}} \neq \mu_{\text{Vehicle}}$$

Where μ is the mean change from baseline at considered visit within the given treatment.

This hypothesis will be tested exploratory at a 5% level of significance with an Analysis of the Covariance (ANCOVA) with treatment and respective baseline value in the model. The Least-squares means estimate of the treatment effect and the treatment group difference (both with 95% confidence intervals) will be reported. P-values will be rounded to three decimal places. If a p-value is less than 0.001 it will be reported as "<0.001". Due to the high numbers of observations, the assumption of normality is assumed.

The analysis will be performed for the following endpoints:

- Change from Baseline in Sande Frequency and Severity Score at Week 8 (LOCF) for the FAS as exploratory primary efficacy analyses
- Change from Baseline in Sande Frequency and Severity Score at Week 8 (LOCF) for the PPS as supportive to primary efficacy analyses

- Change from Baseline in Sande Frequency and Severity Score (without imputation) at Week 4, Week 8 and Week 12 for the FAS as supportive to primary efficacy analyses
- Change from Baseline in Corneal and Conjunctival staining at Week 4, Week 8 and Week 12 for the FAS as well as PPS as exploratory secondary efficacy analyses
- Change from Baseline in TFBUT at Week 4, Week 8 and Week 12 for the FAS as well as PPS as exploratory secondary efficacy analyses
- Change from Baseline in Wetting Distance (5 minutes) at Week 8 for the FAS as well as PPS as exploratory secondary efficacy analyses.

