9.2.1.3 Multiple Comparisons/Multiplicity

Due to this being an exploratory study, no adjustment of any p-values will be made to account for inflation of the Type 1 error rate arising from multiple comparisons or multiple endpoint testing.

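### Does the SAP need a rule for the case where only one of the two primary SANDE scores reaches p<0.05?

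*SAP*

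**What the plan says.** SAP 8.2.7 defines the primary endpoint as two variables, "Change from Baseline in Sande frequency score at Week 8" and "Change from Baseline in Sande severity score at Week 8". It neither ranks nor combines them.

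SAP 9.2 applies the same ANCOVA (treatment and baseline value) to each listed endpoint at an exploratory 5% level. It requires least-squares means, the group difference, 95% confidence intervals and p-values. The first item on its list is "Change from Baseline in Sande Frequency and Severity Score at Week 8 (LOCF) for the FAS as exploratory primary efficacy analyses". SAP 10.5.1 adds descriptive summaries of both scores and says that "The exploratory p-value and estimates for treatment effect as well as treatment group difference resulting from the ANCOVA analysis" will be reported as well. In the SAP 12 table list, Tables 14.2-1.1 and 14.2-1.2 cover the SANDE scores together.

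On sample size, Protocol 10.2 and SAP 4.6 make the same assumption for severity and for frequency: mean changes of -30 and -20, SD 20, 80% power, two-sided 5% t-test. SAP 4.6 adds: "The Type I error probability associated with this test of this null hypothesis is 0.05".

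On the standing of the tests, Protocol 10.2 states that "no adjustment has been made for multiplicity of SANDE parameters" and notes that the actual analysis will be descriptive. SAP 4.7 records that intervals and tests were added at the sponsor's request: "These inferential procedures will be purely exploratory without adjusting for type I error rate". SAP 9.2.1.3 repeats that "no adjustment of any p-values will be made to account for inflation of the Type 1 error rate".

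**The concern.** Two primary variables, each with its own 5% test, can disagree. In a confirmatory trial the plan would have to say whether one score is enough or both are needed, because the type I error and the power of the trial as a whole depend on that choice. Here no visible section says so. The 80% power and the 0.05 in SAP 4.6 hold for each score, and a reader could take them as properties of a single primary result. The singular p-value in SAP 10.5.1, against the plural in SAP 10.5.2, invites the same reading.

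The apparent risk is selective emphasis. The wording of the primary result would be chosen after unmasking, and the report could lead with whichever score did better. If splits were frequent even when the drug works as assumed, this would not be a remote possibility.

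**Working it through.** **1. The plan's own figure.** Inputs from SAP 4.6: difference 10, SD 20, two-sided alpha 0.05, power 0.80, allocation 2:1.

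- Equal arms: n = 2 × (1.960 + 0.842)² × 20² / 10² = 2 × 7.85 × 4 = 62.8, so 63, as in Protocol 10.2. Its 2:1 conversion gives 0.5 × 63 × 3 = 94.5 and 0.5 × 63 × 1.5 = 47.25.
- Directly at 2:1: vehicle n = 1.5 × 7.85 × 4 = 47.1, so 48, and 96 on rhNGF, as in SAP 4.6.
- Non-central t power per score is 80.2% at 96/48 and 79.5% at 95/47 (100/50 less 5%, rounded down).

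The stated figures are correct as per-score figures.

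**2. How often the scores would split.** P(exactly one significant) = 2 × (per-score power − P(both significant)). P(both) depends on the correlation between the two change scores. The documents do not give it, so it is assumed over a range. Figures are from 2,000,000 simulated trials per setting, with both planned effects true:

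| Assumed correlation | 0 | 0.5 | 0.7 | 0.9 |
|---|---|---|---|---|
| Both significant, 95/47 | 63.2% | 68.1% | 70.6% | 74.4% |
| Exactly one, 95/47 | 32.6% | 22.9% | 17.8% | 10.2% |
| Exactly one, 100/50 | 29.7% | 21.2% | 16.5% | 9.5% |
| Exactly one, 95/47, residual SD 18 (assumed ANCOVA gain) | 22.4% | 16.5% | 12.9% | 7.5% |
| Exactly one, no true effect | 9.5% | 8.1% | 6.7% | 4.1% |

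Check at correlation 0: 2 × 0.795 × 0.205 = 32.6%. At 96/48 a normal approximation gives about 7% at correlation 0.95 and 0% at 1. The plan's assumptions therefore do not fix the frequency. Zero correlation is also an implausible end of the range, since one patient answers both questions about the same symptoms at the same visit.

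**3. What a split would look like.** At 95/47 the standard error of a difference is 20 × √(1/95 + 1/47) = 3.57. With 140 degrees of freedom the 5% line lies at about 1.977 × 3.57 = 7.1 mm, only 2.9 mm below the assumed 10 mm. Ordinary sampling variation can put two similar estimates on opposite sides of it. In 1,000,000 simulated trials per setting, among splits:

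| Assumed correlation | 0.7 | 0.9 |
|---|---|---|
| Non-significant score still favours rhNGF | 99.9% | 100% |
| Its p is below 0.10 | 52% | 70% |
| Its p is below 0.20 | 82% | 95% |
| Median gap between the two estimates | 3.2 mm | 1.9 mm |

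Even at correlation 0, the non-significant score favours rhNGF in 99% of splits. Two estimates with their intervals, which SAP 9.2 already requires, describe such a result well.

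**4. What depends on the split.** In the sections set out above, no claim of success or failure rests on p<0.05. The protocol expected a descriptive analysis, and the SAP added the tests as exploratory. A decision rule is missing only where a decision is to be made, and here there is none. SAP 9.2 and 10.5.1 give no option to omit a score or place one above the other.

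**The case for a change.** The strongest counter-argument is that being exploratory does not settle the matter. The no-adjustment statements concern type I error; they do not say how a discordant primary result will be summarised. The protocol foresaw description only, so the possibility of a split entered with the tests that the SAP added, and the SAP would be the natural place to address it. One sentence written before unmasking would cost nearly nothing.

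The omission stands: no visible section words a split result. The arithmetic also stands, given an assumed correlation. Two attachments to the SAP, the table shells and the Note to File on the SANDE questionnaire, are not available here. The SAP describes the note as dealing with administration instructions, so it cannot be assumed to settle the wording.

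The step from omission to error does not stand. The feared harm is selective emphasis in a report that must show both scores in full. Protocol 14.5 states the aim of objective, accurate and balanced reporting and covers negative and inconclusive results; Protocol 14.10 requires a report that complies with ICH E3. These are general provisions, but they address that harm. The singular p-value in SAP 10.5.1 is loose drafting: SAP 9.2 names both scores. Marking the power in SAP 4.6 as per score would add little, since the assumption is already stated for severity and frequency alike.

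**Conclusion.** The concern does not hold. The missing sentence is a matter of report wording. If the sponsor follows the plan exactly, both SANDE scores appear with estimates, intervals and p-values, labelled exploratory and unadjusted, and no stated result is wrong.

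The chance of a split under the planned effect runs from about 33% at zero correlation to about 7% at 0.95. Calling it common therefore depends on a correlation that the plan does not give. At correlations of 0.7 and 0.9, most splits would be near-agreements on either side of the 0.05 line.

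This conclusion rests on the declared exploratory status. If the same pair of endpoints were used to support a confirmatory claim, a rule on one score or both would be needed.

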10.5.2 Secondary Efficacy Analysis

The secondary endpoints Corneal Staining, Conjunctival Staining, TFBUT as well as Wetting Distance at 5 minutes (absolute values as well as changes from baseline) will be summarized descriptively by treatment group and study visit for the study eye. The exploratory p-values and estimates for treatment effect as well as treatment group difference resulting from the ANCOVA analysis specified in section 9.2 will be reported in addition. This analysis will be performed on the FAS and will be repeated on the PPS for supportive purposes.

Listing on secondary efficacy endpoints including assessments for study eye and non-study eye will be provided for FAS, in addition.

10.5.3 Exploratory Efficacy Analysis

The exploratory endpoint MMP-9 Detection will be summarized descriptively by treatment group and study visit for study-eye assessments of patients in the FAS. A shift table is provided summarizing the shift between Week 8 and Baseline Assessment. The analyses will be performed on the FAS. MMP-9 results will be listed in addition.

10.6 Safety Results

10.6.1 Adverse Events

10.6.1.1 Brief Summary of Adverse Events

Reporting of AEs is focused to treatment emergent AEs.

An overview of AEs, TEAEs, TEAEs during Treatment Period, TEAEs during Follow-up Period, TEAEs leading to premature withdrawal of the Study Treatment, TEAEs leading to study discontinuation, serious TEAEs, treatment related TEAEs, treatment related serious TEAEs, TEAEs of special interest and Mild, Moderate and Severe TEAEs will be given by study treatment and overall for patients in the SAF. For each events, the number and percentages of patients with at least one event as well as the total number of events will be provided.

10.6.1.2 Display of Adverse Events

Adverse event descriptive tables will be summarized separately for each study treatment and overall.

They will be summarized on a per-patient basis (i.e. if a patient reported the same event repeatedly the event will be counted only once at the specific level of display). Absolute counts (n) and percentages (%) will be presented for the number of patients with at least one Adverse event, and per SOC and per PT within SOC, for the SAF. Percentages will be based on the number of patients in the population. In addition number of events will be provided.

Descriptive tables will be ordered by descending frequency of the overall number of patients within each SOC regardless of treatment group, and then ordered within each SOC by the overall number of patients within each PT regardless of treatment group. In the event of equal frequencies tables will be ordered by active treatment frequency and then alphabetically.

The following tables will be provided:

- Non-TEAE
- TEAEs
- TEAEs by severity.
- Treatment related TEAEs.
- Serious TEAEs.
- Treatment related serious TEAEs
- TEAEs that occur with a relative frequency in the active treatment of at least twice the relative frequency in the vehicle group.
- TEAEs leading to premature withdrawal of the Study Treatment.
- TEAEs leading to study discontinuation.
- TEAEs during Treatment Period
- TEAEs during Follow-up Period.

10.6.1.3 Listings of Adverse Events

Listings will present all Adverse Event data for the SAF by patient.

In addition specific listings will be created for:

- TEAEs leading to premature withdrawal of study treatment
- TEAEs leading to study treatment interruption
- Serious AEs

Corrective procedures as documented on the eCRF page 'Corrective Procedures Related to AE' will be listed for all patients in the SAF.

10.6.2 Clinical Laboratory Evaluation

A Listing will be provided for patients in the SAF displaying the results of pregnancy tests at Baseline and Week 8 as documented on the eCRF Page 'Urine Pregnancy Test'.

10.6.3 Best Corrected Visual Acuity

BCDVA score and logMAR (absolute values as well as changes from baseline) will be summarized descriptively by treatment group and study visit for the study eye as well as the non-study eye. This analysis will be performed on the SAF. All BCDVA data will be listed.

10.6.4 Slit Lamp Examination

All grading assessments of different eye structure (excluding assessment for Other structures) will be summarized descriptively by treatment group and study visit for the study eye as well as the non-study eye. This analysis will be performed on the SAF.

All data recorded on the eCRF page 'Slit Lamp Examination (Biomicroscopy)' will be listed.

10.6.5 External Ocular Examinations

All evaluations of the motility of extraocular muscle Right and Up, Right, Right and Down, Left and Up, Left, Left and Down will be summarized descriptively by treatment group and study visit for the study eye as well as the non-study eye. This analysis will be performed on the SAF. These data will also be listed.

Incidences of proven eyelid deformity/abnormality, abnormal motor function of eyelids, corneal exposure in case of closed eyelid, proven punctual occlusion, punctual plugs, thermal or surgical occlusion or other punctual occlusion will be presented by treatment group and study visit for the study eye as well as the non-study eye.

Incidences will be calculated as number and percentages of affected patients. The analysis will be performed on the SAF. Moreover, these data will be listed.

11 References

1. Holladay, JT (1997) Proper Method for Calculating Average Visual Acuity. *Journal of Refractive Surgery*, 13, pp. 388-391.
2. Lemp MA. Report of the National Eye Institute/Industry Workshop on clinical trials in dry eye. *CLAO J*1995, 21(4):221–32.

12 Tables, Listings and Figures

Details on Tables and Listings (TLFs) will be provided in a separate document and are attached as appendix to this SAP.

TLF Number	Title
List of Tables	
Table 14.1-1.1	Summary of Patient Disposition
Table 14.1-1.2	Summary of Study Discontinuation (Enrolled Set)
Table 14.1-2.1	Summary of Protocol Deviations (FAS)
Table 14.1-3.1	Summary of Demographic Data (Enrolled Set)
Table 14.1-4.1	Summary of History of Dry Eye Disease (Enrolled Set)
Table 14.1-5.1	Summary of Medical History (Enrolled Set)
Table 14.1-6.1	Summary of Prior medications (Enrolled Set)
Table 14.1-6.2	Summary of Concomitant Medications (Enrolled Set)
Table 14.1-7.1	Summary of Exposure (SAF)
Table 14.1-8-1	Summary of Treatment Compliance (FAS)
Table 14.2-1.1	Summary of Sande Scores (LOCF) (FAS)
Table 14.2-1.2	Summary of Change from Baseline of Sande Scores (LOCF) (FAS)
Table 14.2-1.3	Summary of Sande Scores (LOCF) (PPS)
Table 14.2-1.4	Summary of Change from Baseline of Sande Scores (LOCF) (PPS)
Table 14.2-2.1	Summary of Sande Scores by Visit (Observed) (FAS)
Table 14.2-2.2	Summary of Change from Baseline of Sande Scores by Visit (Observed) (FAS)
Table 14.2-3.1	Summary of Secondary Efficacy Endpoints by Visit (FAS)
Table 14.2-3.2	Summary of Change from Baseline of Secondary Efficacy Endpoints by Visit (FAS)
Table 14.2-3.3	Summary of Secondary Efficacy Endpoints by Visit (PPS)
Table 14.2-3.4	Summary of Change from Baseline of Secondary Efficacy Endpoints by Visit (PPS)
Table 14.2-4.1	Summary of MMP-9 levels by Visit (FAS)
Table 14.2-4.2	Shift Table of MMP-9 levels (FAS)
Table 14.3.1-1.1	Overall Summary of Adverse Events (SAF)
Table 14.3.1-2.1	Summary of Non-TEAEs by System Organ Class and Preferred Term (SAF)
Table 14.3.1-3.1	Summary of TEAEs by System Organ Class and Preferred Term (SAF)
Table 14.3.1-4.1	Summary of Treatment Related TEAEs by System Organ Class and Preferred Term (SAF)
Table 14.3.1-5.1	Summary of Serious TEAEs by System Organ Class and Preferred Term (SAF)
Table 14.3.1-6.1	Summary of Serious Treatment Related TEAEs by System Organ Class and Preferred Term (SAF)

TLF Number	Title
Table 14.3.1-7.1	Summary of TEAEs with a Relative Frequency in the Active Treatment Group of At Least Twice the Relative Frequency in the Vehicle group by System Organ Class and Preferred Term (SAF)
Table 14.3.1-8.1	Summary of TEAEs Leading to Premature Withdrawal of the Study Treatment by System Organ Class and Preferred Term (SAF)
Table 14.3.1-9.1	Summary of TEAEs Leading to Study Discontinuation by System Organ Class and Preferred Term (SAF)
Table 14.3.1-10.1	Summary of TEAEs during Treatment Period by System Organ Class and Preferred Term (SAF)
Table 14.3.1-11.1	Summary of TEAEs during Follow-Up Period by System Organ Class and Preferred Term (SAF)
Table 14.3.1-12.1	Summary of TEAEs by Severity, System Organ Class and Preferred Term (SAF)
Table 14.3.2-1.1	Summary of BCDVA score (SAF)
Table 14.3.2-1.2	Summary of Change from Baseline of BCDVA (SAF)
Table 14.3.2-2.1	Summary of logMAR (SAF)
Table 14.3.2-2.2	Summary of Change from Baseline of LogMAR (SAF)
Table 14.3.3-1.1	Summary of Slit Lamp Examination (SAF)
Table 14.3.4-1.1	Summary of Motility of Extraocular Muscle (SAF)
Table 14.3.4-2.1	Summary of Appearance and Function of Eyelid (SAF)
List of Listings	
Listing 16.1.7-1.1	Randomized Allocation to Treatment and assigned kit numbers (Enrolled Set)
Listing 16.2.1-1.1	Listing of Screening Failure
Listing 16.2.1-1.2	Listing of Study Completion (Enrolled Set)
Listing 16.2.2-1.1	Listing of Protocol Deviations (Enrolled Set)
Listing 16.2.2-1.2	Listing of Inclusion Criteria Deviations at Baseline (Enrolled Set)
Listing 16.2.2-1.3	Listing of Exclusion Criteria Deviations at Baseline (Enrolled Set)
Listing 16.2.3-1.1	Listing of Allocation to Analysis Sets (Enrolled Set)
Listing 16.2.4-1.1	Listing of Demographic Data (Enrolled Set)
Listing 16.2.4-2.1	Listing of History of Dry Eye Disease (Enrolled Set)
Listing 16.2.4-3.1	Listing of Medical History (Enrolled Set)
Listing 16.2.4-4.1	Listing of Prior and Concomitant Medications (Enrolled Set)
Listing 16.2.4-4.2	Listing of Artificial Tear Monitoring (Enrolled Set)
Listing 16.2.5-1.1	Listing of Exposure and Treatment Compliance (SAF)
Listing 16.2.5-1.2	Listing of Treated Eyes, Self Administration and Diary summary information (SAF)
Listing 16.2.5-1.3	Listing of Patient Diary Entries (SAF)
Listing 16.2.6-1.1	Listing of Sande Scores (FAS)
Listing 16.2.6-2.1	Listing of Ocular Surface Staining: Corneal Staining (FAS)

TLF Number	Title
Listing 16.2.6-2.2	Listing of Ocular Surface Staining: Conjunctival Staining (FAS)
Listing 16.2.6-2.3	Listing of TFBUT, Schirmer Tear Test and MMP-9 (FAS)
Listing 16.2.7-1.1	Listing of Adverse Events (SAF)
Listing 16.2.7-1.2	Listing of TEAEs Leading to Premature Withdrawal of Study Treatment (SAF)
Listing 16.2.7-1.3	Listing of TEAEs Leading to Study Treatment Interruption (SAF)
Listing 16.2.7-1.4	Listing of Serious AEs (SAF)
Listing 16.2.7-2.1	Listing of Action taken due to AEs (SAF)
Listing 16.2.7-2.2	Listing of Corrective Procedures Related to AEs (SAF)
Listing 16.2.8-1.1	Listing of Urine Pregnancy Test (Females in SAF)
Listing 16.2.9-1.1	Listing of BCDVA assessments (SAF)
Listing 16.2.9-1.2	Listing of BCDVA score, Snellen Scale and logMAR (SAF)
Listing 16.2.10-1.1	Listing of Slit Lamp Examination – Part I (SAF)
Listing 16.2.10-1.2	Listing of Slit Lamp Examination – Part II (SAF)
Listing 16.2.11-1.1	Listing of Motility of Extraocular Muscle (SAF)
Listing 16.2.11-2.1	Listing of Appearance and Function of Eyelids (SAF)

13 Appendices

Statistical Analysis Plan: Tables, Listings and Figures Mock Shells Attachment (Separate Document)

Note to File: “NGF0216 Sande Questionnaire Endpoints”, dated 25SEP2017, that clarifies the administration instructions of the SANDE questionnaire.
